6.4.5 Virology

Assay methodology and procedures will be described in a Laboratory Manual to be finalised before the samples are collected. Samples will be shipped to and analysed by PPD Central Laboratory.

6.4.6 Drugs of Abuse Testing

History (within last 2 years) of current prescription drug or substance abuse, including alcohol, considered significant by the Investigator is an exclusion criterion for this study (see Section 4.3). Drug abuse is a patterned use of a substance in which the patient uses amounts or methods that are harmful to themselves or others during the study period. If the medical history suggests such abuse, then the Investigator should consider whether the patient meets the exclusion criteria. Drugs of abuse screening, including breath test, may be performed at the Investigator's discretion.

6.4.7 Vital Signs

Vital signs will be assessed throughout the study. On IMP administration Days 1 (Week 0), 29 (Week 4), 57 (Week 8), 85 (Week 12), and 113 (Week 16), vital signs will be measured pre-injection and at 15-, 30-, and 60-minutes post-injection. On all other IMP administration days, vital signs will be measured pre-injection and 30 minutes post-injection.

Evaluations of systolic and diastolic blood pressure, heart rate, and tympanic temperature will be performed (other methods may be used but they must be consistently used throughout the study for each individual patient). Heart rate and blood pressure will be taken after 5 minutes in the supine position.

Any changes from Baseline in blood pressure and heart rate findings judged to be clinically significant by the Investigator will be recorded as AEs. In such cases, vital signs will be repeated at appropriate intervals until they return to Baseline or to a level deemed acceptable by the Investigator or until the abnormality can be explained by an appropriate diagnosis.

Vital signs may be repeated a maximum of once where initial results are outside of the limits defined in the inclusion/exclusion criteria and only provided the initial result is considered a temporary anomaly and there is a documented explanation as to the likely cause of the result.

6.4.8 12-lead ECG

Standard 12-lead ECGs will be performed throughout the study after the patient has been supine for at least 5 minutes. All ECGs should be recorded with the patient in the same physical position. The ECG should be obtained either prior to the time of blood collection, or at least 15 minutes afterwards.

The ECG traces are to be reviewed by a qualified physician at the study site (physician to sign, date and record interpretation on ECG trace). The Investigator will enter a signed and dated clinical interpretation of the ECG trace in the CRF. Any ECG traces on heat sensitive paper must be photocopied before archiving.

6.4.9 Local Skin Reactions

Light pressure will be applied at the injection site and any pain, itchiness, tenderness, erythema, and induration will be recorded in the eCRF. Pain, itchiness and tenderness will be assessed according to the following scale:

Definitions of pain and tenderness:

- None nothing.
- Mild easily tolerated.
- Moderate interferes with daily activities.
- Severe prevents normal everyday activities or sleep.

The largest diameter of erythema and induration will be measured using a ruler, or a template supplied by the Sponsor.

6.5 Pharmacokinetic and Anti-drug Antibodies Assessments

6.5.1 Pharmacokinetic Procedures

Blood samples will be withdrawn periodically for KY1005 assay. Pharmacokinetic and ADA samples will be collected from all patients including those receiving Placebo.

6.5.1.1 Pharmacokinetic Sampling Schedule

Serum concentrations of KY1005 will be assessed from blood samples taken during the study using validated enzyme-linked immunosorbent assay (ELISA) bioanalytical methods. Assay methodologies and procedures will be described in analytical plans to be finalised before the start of sample analysis.

Samples will be collected at the timepoints specified in the Schedule of Assessments (see Table 6-1, Table 6-2 and Table 6-3). On IMP administration days, samples for serum concentration of KY1005 will be withdrawn pre-dose.

Tolerances for deviation from the nominal time of sampling are provided in the schedule of assessments (visit window). These tolerances indicate the best time to allow interpretation of data. However, samples taken outside these tolerances will be evaluated so should be taken. The exact date and time of sampling will be recorded. Samples may also be drawn for serum concentration, with prior agreement with the Medical Monitor, at unscheduled times.

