6.5.1.3 Pharmacokinetic Parameter Derivation

The following PK values will be derived for each patient receiving KY1005 and all KY1005 regimens:

• C_{max} following the first, or any doses where sampling permits. Peak concentrations following any doses where sampling permits.

- t_{max} following the first, or any doses where sampling permits.
- C_{min} following the first, second, third, fourth and any doses where sampling permits.

1-Mar-2022

Version number: 1

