9.1.2.1 Re-challenge

Reinitiation of intervention with the IMP will be done under close and appropriate clinical and/or laboratory monitoring once the Investigator will have considered according to his/her best medical judgment that the responsibility of the IMP(s) in the occurrence of the concerned adverse event was unlikely and if the selection criteria for the study are still met (refer to Section 4).

If there is to be a delay to any dosing of IMP outside of the permitted visit windows as per the Schedule of Assessments (Section 6.1), the Investigator must consult with, and receive written confirmation that dosing can be rescheduled from, the Medical Monitor.

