### 10.2. Serum Concentrations

Blood samples will be collected at the following time points for PK assessment:

Predose (Day 1), Day 8, Day 15, Day 29, Day 57, Day 85, Day 113, Day 120, Day 141, Day 169, Day 176, Day 197, Day 225, Day 253, Day 281, Day 309, Day 337, and Day 365.

PK collections that have an actual sampling time that deviates from the predefined collection time window ( $\pm 3$  days) or that are collected post-dose (except at Day 8, Day 15, Day 120 and D176) will be flagged in the data listings and excluded from the calculation of concentration summary statistics. In addition, when patients withdraw from the treatment earlier and still have PC collection at one or more later visits, the pre-dose PC data collected from 25 to 31 days post last dose (ie, corresponding to the time window of the next scheduled administration) are still included in the analysis.

Individual serum concentrations will be expressed in  $\mu\text{g/mL}$  and will be presented in data listings and summarized separately using descriptive statistics (number of observations, arithmetic mean, SD, CV%, median, minimum, and maximum) by treatment group and visit weeks. Serum concentration summaries will also be presented by ADA status (e.g. ADA positive, ADA negative), where data permit.

Individual serum concentrations will be plotted by actual time on linear scale. Mean serum concentrations will be plotted by treatment and visit weeks on linear scale with all dose levels overlaid on the same plots. Mean serum concentration plots will also be presented by ADA status (e.g. ADA positive, ADA negative), where data permit.

Serum concentrations will be reported to 3 significant figures in summary statistics except CV%, which will be reported to 1 decimal place.

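### For patients still on treatment, SAP 10.2 selects PK samples by nominal study day only, so samples after a missed dose enter the by-visit pre-dose means; its ±3-day window also departs from the schedule's ±1 at Days 120 and 176

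*Protocol*

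**What the plan says.** **Protocol.** Section 6.5.1.1 states: "Tolerances for deviation from the nominal time of sampling are provided in the schedule of assessments (visit window". In Tables 6-1 to 6-3 that window is 0 on Day 1, ±1 day on Days 120 and 176, and ±3 days on every other PK day. The same section adds that "samples taken outside these tolerances will be evaluated so should be taken". Dosing is every 28 days (1.7). Doses can be missed without leaving treatment: 9.1.2 and Appendix 14 (17.14) both provide for temporary interruption. Section 9.1.2.1 deals with late doses ("If there is to be a delay to any dosing of IMP outside of the permitted visit windows") by requiring written agreement from the Medical Monitor.

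**SAP.** Section 10.2 lists the PK days as study days, which 4.4.4 counts from the first administration. It then says: "PK collections that have an actual sampling time that deviates from the predefined collection time window", given as ±3 days for all of them, "will be flagged in the data listings and excluded from the calculation of concentration summary statistics". Samples taken after dosing are treated the same way, except on Days 8, 15, 120 and 176. One criterion rests on time since dose: for patients who withdraw from treatment early, "the pre-dose PC data collected from 25 to 31 days post last dose" stay in the analysis. Table 15 assigns PK samples to visits with its own windows: Days 118 to 131 for Week 17 and Days 174 to 187 for Week 25.

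**The concern.** A pre-dose concentration can be interpreted only if the time since the last dose is known and similar across the patients being averaged. For a patient who stays on treatment, SAP 10.2 checks the calendar and not the dosing history. A sample taken on schedule after a skipped dose passes the check, although it comes about twice as long after dosing as the samples it is averaged with.

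Serum concentration is a secondary endpoint (Protocol 2.1.2, SAP 2.2). The by-visit means, by treatment group and by ADA status, are the SAP's tabulated description of exposure under the four regimens. A mean that mixes two post-dose intervals understates pre-dose exposure.

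The second issue is a mismatch between documents. The window that the SAP calls predefined is not the one in the protocol's schedule at Days 120 and 176, and Table 15 differs from both.

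**Working it through.** **Rule.** For a sample on day S with window w, after a dose on day D with window v, the days since dose run from (S − w) − (D + v) to (S + w) − (D − v). The dose window v is 0 on Day 1 and 3 afterwards.

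**The SAP's own figure.** The dosing interval is 28 days, so 28 − 3 = 25 and 28 + 3 = 31. The 25-to-31-day criterion is reproduced.

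**Pre-dose samples, all doses given (w = 3).**
- Day 29 after Day 1: 26 − 1 = 25 to 32 − 1 = 31 days.
- Day 57 after Day 29: 54 − 32 = 22 to 60 − 26 = 34 days. Later visits give the same range.

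**Pre-dose samples, preceding dose missed, patient continues (w = 3).**
- Day 57, last dose Day 1: 54 − 1 = 53 to 60 − 1 = 59 days.
- Day 85, last dose Day 29: 82 − 32 = 50 to 88 − 26 = 62 days. Later visits give the same range.

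These samples lie within ±3 days of the nominal day and were taken before dosing, so SAP 10.2 keeps them. The two groups do not overlap: the longest compliant interval is 34 days and the shortest after a missed dose is 50.

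**Effect on the mean.** If a fraction f of the contributing patients missed the preceding dose, and their concentration is on average r times that of the others, the mean changes by −f(1 − r). The documents give neither f nor the half-life that determines r. As an illustration only, assume log-linear decline near steady state and a half-life of 14 to 35 days. Then r = 2^(−28/14) = 0.25 to 2^(−28/35) = 0.57, and the change is −0.75f to −0.43f. The direction is clear; the size is not.

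**Days 120 and 176 (doses on Days 113 and 169, each ±3).** For Day 176 this concerns re-randomised patients who continue on KY1005.

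| Sample window | Day 120 arithmetic | Days post-dose, both visits |
|---|---|---|
| Schedule, ±1 | 119 − 116 to 121 − 110 | 3 to 11 |
| SAP 10.2, ±3 | 117 − 116 to 123 − 110 | 1 to 13 |
| SAP 10.2 and Table 15 together | 118 − 116 to 123 − 110 | 2 to 13 |
| Table 15 alone | 118 − 116 to 131 − 110 | 2 to 21 |

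The third row arises because Table 15 assigns Day 117 to Week 16 (Days 100 to 117) and Day 173 to Week 24 (Days 156 to 173). With the dose on its nominal day, the spans are 4 to 10 days (±3) and 6 to 8 days (±1).

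**Other post-dose samples.** Because Day 1 has no window, Day 8 is 8 ± 3 − 1 = 4 to 10 days post-dose and Day 15 is 15 ± 3 − 1 = 11 to 17 days.

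**The case against.** The case for leaving the SAP alone has several sound parts.

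- **A time-since-dose rule exists.** A reader might infer that the SAP ignores dosing history altogether. It does not: the 25-to-31-day criterion covers patients who withdraw from treatment. The gap is confined to missed or late doses in patients who continue.
- **Other PK output is planned.** All concentrations are listed, individual profiles are plotted by actual time (SAP 10.2), and population PK has a separate plan (SAP 10). The by-visit means are therefore not the only PK results. The SAP does not call them troughs, and it derives no Cmin: 10.4 is marked not applicable, although Protocol 6.5.1.3 says "The following PK values will be derived for each patient receiving KY1005 and all KY1005 regimens" and lists Cmin.
- **Evaluated need not mean averaged.** A reader might see a contradiction between the protocol's promise to evaluate out-of-tolerance samples and their exclusion in SAP 10.2. A sample that is assayed, flagged and listed has been evaluated in a reasonable sense.
- **The wide post-dose spread is mostly not the SAP's doing.** The 1-to-13-day span holds only at Days 120 and 176, with dose and sample at opposite extremes. The schedule's own ±1 already allows 3 to 11 days, and sites remain bound by ±1.
- **Late doses.** One might infer that true 28-day samples are dropped after a rescheduled dose. That requires later visits to move with the dose, which the documents do not say.

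These arguments narrow the point. They do not meet the missed-dose case: the by-visit tables are still a planned summary of a secondary endpoint, and as written they include samples taken 50 days or more after dosing.

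**Conclusion.** The point holds in this limited form. Followed as written, SAP 10.2 admits pre-dose samples taken 53–59 days (Day 57) or 50–62 days (Day 85 onward) after the last dose into means otherwise based on 22–34 days, whenever a continuing patient has missed the preceding dose. This biases the affected means downward. The size depends on half-life and missed-dose rate, neither of which the documents give, and nothing in them shows that interruptions differ between arms. The conclusion rests on reading the ±3-day window as centred on the study days that SAP 10.2 lists, which is the natural reading.

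The window mismatch is a separate and smaller matter. It affects two PK days, adds 2 days at each end of the range (1–13 instead of 3–11), and does not cause the missed-dose problem. Neither issue touches the efficacy analyses.

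**What to change.** **In SAP 10.2, for all patients on active dosing:** exclude a sample from the by-visit pre-dose summaries if the preceding scheduled dose was not given, or was given so late that the actual time since last dose falls outside the range implied by the visit windows. That range is 25–31 days at Day 29 and 22–34 days from Day 57. Extending the 25-to-31-day criterion to everyone would be too strict, because from Day 57 it would discard samples from fully compliant patients.

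**For Days 120 and 176:** use the schedule's ±1 day, or state a range around 7 days after the actual dose, and bring Table 15 into line. Only the second option also removes a sample taken after a missed Day 113 or Day 169 dose.

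**Keep** every excluded sample in the listings, the actual-time plots and the population PK data.

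**Cost:** SAP wording and programming. Sampling dates and times are already recorded (Protocol 6.5.1.1), and the PK sets already require documented dosing dates (SAP 4.3.6 and 4.3.7). The downside is slightly fewer samples at some visits.

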6.5.1.2 Pharmacokinetic Sample Preparation and Shipment

The details of blood volume, type of tube, sample handling, storage and dispatch are described in the Laboratory Manual.

6.5.1.3 Pharmacokinetic Parameter Derivation

The following PK values will be derived for each patient receiving KY1005 and all KY1005 regimens:

• C_{max} following the first, or any doses where sampling permits. Peak concentrations following any doses where sampling permits.

- t_{max} following the first, or any doses where sampling permits.
- C_{min} following the first, second, third, fourth and any doses where sampling permits.

1-Mar-2022

Version number: 1

6.5.2 Anti-drug Antibody Procedures

Blood samples will be withdrawn periodically for anti-KY1005 antibody assays.

6.5.2.1 Anti-drug Antibody Sampling Schedule

[figure not shown]
Serum titres of anti-KY1005 antibodies will be assessed in blood samples taken during the study using a validated bioanalytical method. Characterisation of positive ADA samples, eg, KY1005 neutralising capacity, may be performed if required.

Samples will be collected at the timepoints specified in the Schedule of Assessments (see Table 6-1, Table 6-2, Table 6-3 and Table 6-4) and will be withdrawn before injection of IMP. Tolerances for deviation from the nominal time of sampling are provided in the schedule of assessments (visit window). These tolerances indicate the best time to allow interpretation of data. However, samples taken outside these tolerances will be evaluated and should therefore be collected. The exact date and time of sampling will be recorded on the eCRF.

6.5.2.2 Anti-drug Antibody Sample Preparation and Shipment The details of blood volume, type of tube, sample handling, storage and dispatch are described

[figure not shown]
in the Laboratory Manual.

6.6 Assessment of Pharmacodynamics Markers

1-Mar-2022

	·
6.7 Total Blood Volume	

7 USE OF BIOLOGICAL SAMPLES AND DATA FOR FUTURE RESEARCH

Future research may help further the understanding of disease subtypes, disease biology, related conditions, drug response and toxicity, and can help identify new drug targets or biomarkers that predict patient response to treatment. Therefore, data and biological samples will be stored and used for future research when consented to by participants unless prohibited by local laws or IRBs/IECs (in such case, consent for future use of sample will not be included in the local ICF).

Data and samples will be used in compliance with the information provided to patients in the section of the ICF related to future research.

All study patient data and samples will be coded such that no patient direct identifiers will be linked to them. Coded data and samples may be transferred to a Sponsor site (or a sub-contractor site), which may be located outside of the country where the study is conducted. The Sponsor adopts safeguards for protecting participant confidentiality and personal data.

The samples will be stored for a maximum of 25 years after the end of the study. Any samples remaining at the end of retention period will be destroyed. If a participant requests destruction of his/her samples before the end of the retention period, the Investigator must notify the

Sponsor (or its CRO) in writing. In such case, samples will be destroyed, and related coded data will be anonymised unless otherwise required by applicable laws.

Study patient coded data will be stored for future research for up to 25 years after the end of the study. If data are still considered of important scientific value after this period, coded data already available will be anonymised unless otherwise required by applicable laws (the same will apply to the data of a study patient who has requested the destruction of his/her samples).

Patient's coded data sets provided to researchers for a specific research project will be available to the researchers for a maximum of 2 years after the end of their specific project (end of project is defined by publication of the results or finalisation of the future research project report).

8 SAFETY MONITORING AND REPORTING

8.1 Definition of an Adverse Event

The ICH E6(R2) Good Clinical Practice Guideline defines an AE as any untoward medical occurrence in a patient or clinical investigation patient administered a pharmaceutical product, which does not necessarily have to have a causal relationship with this treatment. An AE can, therefore, be any unfavourable and unintended sign (including an abnormal laboratory finding), symptom or disease temporally associated with the use of a medicinal (investigational) product, whether or not considered related to the medicinal (investigational) product.

An AE can include an undesirable medical condition occurring at any time, even if no investigational medicinal product has been administered. This includes an exacerbation of pre-existing conditions or events, intercurrent illnesses, drug interaction, or the significant worsening of the indication under investigation that is not recorded elsewhere on the eCRF under specific efficacy assessments. Anticipated fluctuations of pre-existing conditions, including the disease under study, that do not represent a clinically significant exacerbation or worsening are not considered AEs and will not be captured as AEs. Lack of efficacy or failure of expected pharmaceutical action per se will not be reported as an AE or a SAE. Such instances will be captured under the efficacy assessments. However, the signs symptoms and clinical sequelae resulting from lack of efficacy will be reported as an AE/SAE if they fulfil the definition of an AE or SAE.

This definition includes events occurring from the time of the patient giving informed consent until the 140 days after the last dose of IMP.

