5.3.4 Rescue Therapy

No AD rescue therapy is permitted in the first 14 days following randomisation. Any AD rescue therapy administration either topical or systemic during this period will result in permanent discontinuation from the IMP. Bland emollients are not considered rescue therapy for AD, and should be maintained during this period as per protocol.

1-Mar-2022

Version number: 1

If medically unavoidable after Day 14 (ie, to control intolerable AD symptoms), rescue treatment for AD may be provided to study patients at the discretion of the Investigator. For the purpose of efficacy analysis, patients who receive rescue topical treatment during this study treatment period will be considered treatment failures but can continue study treatment if the rescue treatment consists of topical medications only.

If topical corticosteroids (TCS) are needed, it is recommended that the investigator start with the least potent TCS for the face (eg, hydrocortisone 2.5% cream/ointment) and moderately potent TCS for the body (eg, triamcinolone acetonide 0.1% cream/ointment), applied up to twice daily. Where the use of moderate potency topical corticosteroids (TCS) are not considered clinically appropriate, low potency TCS or topical calcineurin inhibitors can be used, however, these should be reserved for problem areas only. Topical PDE4 inhibitors are also permitted.

Participants should use topical rescue therapy only for as long as necessary to control problem areas on a maximum of 2 occasions during study participation, and for a maximum of 2 consecutive weeks on each occasion.

If a patient receives rescue treatment with high potency TCS, systemic corticosteroids or non-steroidal systemic immunosuppressive drugs (cyclosporine, methotrexate, mycophenolate mofetil, azathioprine, etc) or receives more than 2 episodes of topical rescue treatment, study treatment will be immediately discontinued.

Investigators should conduct efficacy and safety assessments immediately before administering any rescue treatment. An unscheduled visit may be required.

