8.1.5 Disease-related events and/or disease-related outcomes not qualifying as AEs or SAEs

Not applicable.

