### 9.1.1 Incidence of Adverse Events

An overall summary of AEs including the counts and percentages of patients will be presented by KY1005 treatment regimen and in the Placebo group for the study periods mentioned in Section 9.1:

- Any AE
- Any SAE
- At least 1 TEAE
- Any related TEAE
- Any severe TEAE
- Any Treatment Emergent SAE
- Any SAE Related to Study Treatment
- Any AE Leading to Treatment Discontinuation
- Any AE Leading to Study Discontinuation
- Any AE Leading to Death
- Any AESI

Below summary tables will be provided by KY1005 treatment regimen and the Placebo group using count and percentages of patients:

- Number (%) of Patients of Pre-treatment Adverse Events by SOC and PT
- Number (%) of Patients with TEAE by SOC and PT from Baseline (Week 0) up to Week 24
- Number (%) of Patients with TEAE by SOC and PT from Week 24 up to Week 68
- Number (%) of Patients with TEAE by SOC and PT from Baseline (Week 0) up to Week 68
- Number (%) of Patients of Post-treatment Adverse Events by SOC and PT
- Number (%) of Patients with TEAE by HLGT, HLT, SOC and PT from Baseline (Week 0) up to Week 24
- Number (%) of Patients with TEAE by HLGT, HLT, SOC and PT from Week 24 up to Week 68
- Number (%) of Patients with TEAE by HLGT, HLT, SOC and PT from Baseline (Week 0) up to Week 68
- SOC Number (%) of Patients of TEAEs by PT from Baseline (Week 0) up to Week 24
- Number (%) of Patients of TEAEs by PT from Week 24 up to Week 68
- Number (%) of Patients of TEAEs by PT with total incidence  $\geq 5\%$  from Baseline (Week 0) up to Week 24
- Number (%) of Patients of TEAEs by PT with total incidence  $\geq 5\%$  from Week 24 up to Week 68
- Number (%) of Patients of TEAEs by PT with total incidence  $\geq 5\%$  from Baseline (Week 0) up to Week 68
- Number (%) of Patients of TEAEs by PT with total incidence from Baseline (Week 0) up to Week 24
- Number (%) of Patients of TEAEs by PT with total incidence from Week 24 up to Week 68

- Number (%) of Patients of TEAEs by PT with total incidence from Baseline (Week 0) up to Week 68
- Incidence Rate per Patient Year Exposed from Baseline (Week 0) up to Week 24
- Incidence Rate per Patient Year Exposed from Week 24 up to Week 68
- Incidence Rate per Patient Year Exposed from Baseline (Week 0) up to Week 68

All AEs and TEAEs will be presented in a listing.

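### Protocol Section 8.1 is inconsistent on when a significant worsening of atopic dermatitis is an adverse event, and the SAP has no TEAE summary without such worsening, so the overall TEAE rates could favour the effective doses

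*Protocol*

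**What the plan says.** Protocol Section 8.1 deals with worsening of the treated disease in one paragraph, in four steps:

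- An adverse event includes "the significant worsening of the indication under investigation that is not recorded elsewhere on the eCRF under specific efficacy assessments".
- Expected variation short of that is left out; this covers fluctuations "that do not represent a clinically significant exacerbation or worsening are not considered AEs and will not be captured as AEs".
- Treatment failure as such is also left out and belongs with the efficacy data: "Lack of efficacy or failure of expected pharmaceutical action per se will not be reported as an AE or a SAE".
- The consequences of treatment failure are then brought back in, because "the signs symptoms and clinical sequelae resulting from lack of efficacy will be reported as an AE/SAE if they fulfil the definition".

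Protocol Section 8.1.5, headed "Disease-related events and/or disease-related outcomes not qualifying as AEs or SAEs", is marked not applicable.

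EASI and IGA are completed on an internet-enabled device (Protocol 6.3.1, 6.3.2). SAP 4.4.5 and 6.2.2 give their source as eCOA, while SAP 6.1 refers to baseline EASI from IRT and eCRF data. Before rescue, "Investigators should conduct efficacy and safety assessments immediately before administering any rescue treatment" (Protocol 5.3.4). The safety follow-up schedule (Protocol Table 6-4) contains no EASI, IGA, BSA or SCORAD.

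Protocol 10.4.2.4.1 calls TEAE incidence the primary safety endpoint. The overall table in SAP 9.1.1 has rows for "At least 1 TEAE", severe TEAEs and adverse events leading to discontinuation. SAP 9.1 gives no rule for worsening of atopic dermatitis, and no overall row leaves it out.

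**The concern.** Read literally, the first step makes adverse event status depend on whether an efficacy score was taken and where it was stored, not on what happened to the patient. The second and fourth steps carry no such condition. Two careful investigators could record the same flare differently, and both could cite Section 8.1.

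The consequence for the safety comparison is separate. Worsening of the treated disease is plausibly commoner where treatment does not work. Any part of it that enters the TEAE count brings lack of efficacy into the safety endpoint. That would lower the overall rates on effective doses relative to placebo and could offset a real excess of other events. The rows at risk are the ones most often quoted: any TEAE, severe TEAE and discontinuation for adverse events.

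**Working it through.** **1. The same event under each rule.** Take a clinically significant flare.

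| Situation | First step of 8.1 | Second and fourth steps of 8.1 |
|---|---|---|
| EASI/IGA scored, device data treated as eCRF | not an AE | second step does not exempt it; fourth makes its signs AEs if the definition is met |
| EASI/IGA scored, device data not treated as eCRF | AE | as above |
| Safety follow-up, no scoring scheduled | AE | as above |

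The third row cannot be dismissed. Patients who stop treatment early and decline remaining visits enter safety follow-up (Protocol 9.1.3). SAP 9.1 counts their TEAEs up to 140 days after the last dose, and SAP 9.1.7 assigns that follow-up to the period in which they stopped. In Part 2, efficacy scoring ends at Week 52 while TEAE tables run to Week 68. So even a site that always applies the first step would switch rules between periods.

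**2. Direction and size.** The plan states no figure to reproduce and no rate of worsening. Let b be the proportion with any other TEAE, w the proportion with significant worsening, and f the share of worsenings entered as adverse events. Assuming independence:

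P(any TEAE) = 1 − (1 − b)(1 − f·w)

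With b equal in both arms, placebo minus active = (1 − b) · f · (w_placebo − w_active).

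Assumed ranges, none from the documents: b 40–60%, w 20–30% on placebo and 8–15% on active.

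- f = 0: difference 0.
- f = 1, smallest: 0.4 × (20 − 15) = 2.0 points.
- f = 1, largest: 0.6 × (30 − 8) = 13.2 points.
- f = 0.5: half of these, 1.0 to 6.6 points.
- Mid-range example, b = 50%, w = 25% v 10%, f = 1: placebo 1 − 0.5 × 0.75 = 62.5%; active 1 − 0.5 × 0.90 = 55.0%; difference 7.5 points with no true safety difference.

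**3. Masking.** Same w, but other TEAEs 50% on placebo and 57.5% on active, a true excess of 7.5 points.

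- f = 0: +7.5 points.
- f = 0.5: active 1 − 0.425 × 0.95 = 59.6%; placebo 1 − 0.5 × 0.875 = 56.25%; +3.4 points.
- f = 1: active 1 − 0.425 × 0.90 = 61.75%; placebo 62.5%; −0.75 points.

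**4. Can the planned tables undo it?** The SOC and PT tables would show the disease terms on their own lines. They do not give the number of patients with any TEAE other than those terms, because patients overlap. In the example, an any-TEAE rate of 62.5% with 25% under the disease term leaves the rate without that term anywhere from 62.5 − 25 = 37.5% (nobody had another event) to 62.5% (everybody did).

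**The case against.** Several points on the other side stand.

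- **A tiered reading is possible.** Disease activity goes to the efficacy data, and only consequences that meet the AE definition in their own right go to the AE form. This is a sensible intention, but the text does not state it. The eCRF condition and the unscored follow-up remain unresolved under it.
- **The bias may be near zero.** If sites treat nearly every flare as already recorded under efficacy, f is close to 0. A reader might infer that TEAE incidence will favour the effective doses; the documents support only that it could.
- **No worsening rate is available.** The Phase 2a EASI 75 results (25.0% on placebo, 51.9–59.3% on KY1005; Protocol Table 1-1) are tempting as evidence. Missing EASI 75 is not worsening, and mean EASI on placebo fell by 49.37% in the same table.
- **Section 8.1.5 is weak evidence.** A reader might take its entry to mean that no disease-related event is exempt. It may be unused template text, or mean only that no separate list was defined. The conflict inside 8.1 does not need it.
- **Site differences are not a bias by themselves.** Under the blind, a site's reading applies to all its arms, so it mainly scales f and adds noise. The tilt comes from unequal worsening between arms.
- **An excess of other events would not be hidden altogether.** SOC/PT, severity and discontinuation tables and full listings are planned, and Protocol 8.1.1 asks for a diagnosis rather than individual signs. This confines the problem to the overall rows.
- **The tables are descriptive.** With 70 per arm, the standard error of 62.5% v 55.0% is √(0.625 × 0.375/70 + 0.55 × 0.45/70) = 8.3 points, so a shift of this size lies within sampling error.

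**Conclusion.** The inconsistency in Protocol Section 8.1 is established from the text and holds without any assumption about rates. Neither document settles whether device-held EASI and IGA scores count as being on the eCRF, or how worsening is handled once efficacy scoring has stopped.

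The effect on the safety comparison is conditional. It needs some worsenings to be entered as adverse events and more worsening on placebo or less effective doses. If both hold, the overall rates tilt towards the effective doses. The 2.0 to 13.2 points for any TEAE rest on assumed rates, independence and every worsening being counted; the true size cannot be known from the documents. The point justifies an inexpensive improvement to the safety summaries and a clarification of the recording rule. It does not show that the planned safety analysis is invalid.

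**What to change.** **SAP.** In 9.1.1, and in the severity and discontinuation summaries (9.1.4, 9.1.5), report any TEAE, severe TEAE and TEAE leading to discontinuation both with and without preferred terms for worsening of atopic dermatitis. Fix the list of terms before unblinding. This needs no new data and separates lack of efficacy from other safety findings for every worsening entered under a listed term, whichever way a site read Section 8.1.

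**Protocol.** Reconcile 8.1 and 8.1.5 into one recording rule that names the data source (eCRF, eCOA or both) and covers follow-up without efficacy scoring. The recording rule alone is not enough. Simply deleting the eCRF condition would count every significant worsening and enlarge the tilt in the overall rows.

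**Passages to reconcile with it.** Protocol 9.1.1 item 8 links adverse event grade to stopping dosing, while 5.3.4 lets patients given only topical rescue continue. Whether a severe flare is entered as an adverse event therefore affects which passage applies. The sponsor must reconcile these with the chosen recording rule; no clinical rule is proposed here.

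**Cost.** A few extra summary rows, a Section 8 clarification and a note to sites.
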